6.1.3.7 Quality Assurance of Interventions

In order to ensure consistency in the education provided to each group, we will audio record 20% of study visit 2 in each group. Key study personnel who did not perform the educational intervention will review the audio recording and score for fidelity. These audio recordings will be strictly used to ensure consistency of the intervention, will not be used to collect data. Audio files will be contained within REDCap.

6.1.4 Management between study visit 2 and 3

Each T1DM participant's will manage his or her glycemic control before and between study visits using insulin as prescribed by their primary endocrinologist. Participants will be instructed to contact the research team and will be removed from the research protocol in the event of any of the following: weight loss more than 10% from baseline or any episode of DKA or severe hypoglycemia.

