2.0 Rationale and Specific Aims

We hypothesize that pediatric patients with T1DM who consume a LCD will have improved HbA1c compared with T1DM patients who consume a standard-carbohydrate diet (SCD). We further hypothesize that differences in lipidemia and quality of life (QOL) between the groups will be minimal. To test our hypotheses, we will employ a pragmatic nutrition education intervention. The study will randomize adolescent patients (ages 13-21 years) to one of three groups (n = 15per group). We will instruct participants to consume a LCD (group 1) or a SCD (group 2), or provide no specific recommendations regarding diet (group 3). We will prescribe isocaloric diets for groups 1 and 2 equaling the estimated energy requirements of the Institute of Medicine⁷. Participants on the SCD intervention will consume 45-65% of total daily caloric intake from carbohydrates, 25-35% from fat and 10-30% from protein. Participants on the LCD intervention will consume 25-35% of total daily intake from carbohydrates, 45-65% from fat and 10-30% from protein. Group 3 will serve as a control that receives the same number of education sessions as groups 1 and 2 to teach general diabetes management but without specific dietary recommendations. This study design will allow for discrimination of the effect of the composition of the diet versus the effect of receiving any nutritional prescription.

Nutrition interventions are effective in producing dietary behavior change among adolescents²⁷, particularly when information and communication technologies (ICT) are incorporated²⁸. Previous brief nutrition interventions teaching LCD or low glycemic index diets in T1DM patients have resulted in appropriate dietary adherence^{29,30}. We will provide both traditional and ICT-based education and monitor dietary adherence with a smart-phone based nutritional tracking tool.

Aim 1 will provide preliminary estimates of improvement HbA1c after a nutrition intervention that teaches a LCD versus education reinforcing a SCD to families of pediatric T1DM patients. To determine the primary outcome—change in HbA1c—we will obtain HbA1c at baseline and at 12 weeks after the nutrition intervention. Additionally, we will quantify glycemic variability using continuous glucose monitoring (CGM) as a secondary outcome. Low rates of severe hypoglycemia, diabetic

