ketoacidosis and growth attenuation have been reported in pediatric T1DM patients on a VLCD¹³, therefore, we anticipate low rates of these adverse events with the LCD intervention.

Aim 2 will provide preliminary estimates of the change in the atherogenic lipoprotein profile in patients on a LCD versus SCD. The primary outcome measure will be change in total LDL-P from baseline to 12 weeks after the nutrition intervention. As secondary outcomes, we will measure the change in other contributors to atherogenic lipoprotein load, such as high-density lipoprotein particle (HDL-P) number, small LDL-P number, and LDL size.

Aim 3 will provide preliminary estimates of the change in QOL in patients on a LCD versus SCD. Participants will complete the PedsQL, a validated QOL measure in T1DM patients, and Problem Areas in Diabetes-Teen (PAID-T), a validated measure of diabetes-specific distress, at baseline (week 0) and at 12 weeks after the nutrition intervention^{31,32}. Additionally, parents of participants will complete the WHO-5 Well-Being Index, a questionnaire for assessing subjective psychological well-being³³, and Problem Areas in Diabetes-Parent Revised version (PAID-PR), a validated measure of perceived parental burden associated with caring for a child with diabetes.³⁴

We will perform an independent samples t-test to compare outcomes between groups, in addition to multilinear regression analysis to account for potentially confounding covariates, such as total daily dose of insulin, weight change, glycemic variability as measured by continuous glucose monitoring (CGM), and age.

This proposed research will be the first prospective study to determine the effect of a LCD intervention on key diabetes outcomes in a pediatric T1DM population. This study will also provide a basis of training for a new pediatric investigator in the conduct of clinical trials under the mentorship of a highly successful mentorship team including [name] and [name].

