6.1.4.2 Text Messaging

Participants will receive text messages 2 to 4 times per week³⁶ that will provide reminders regarding key components of the dietary intervention, encouragement regarding diabetes management, and general positive quotes. The study team will create a bank of 50 text messages for each dietary intervention (LCD and SCD), and participants will receive 2 to 4 of these text messages per week. Examples of message content include: "Try a breakfast high in protein! An omelet with a side of bacon would be a great choice" and "The only way of finding limits of the possible is by going beyond them and into the impossible – Arthur C. Clarke." The text message will be sent using the text messaging feature in RedCap with the Twilio messaging service and will contain no protected health information. Text messaging will continue until participants have completed study visit 3.

6.1.5 Telephone Visits (Weeks 2, 4, and 8)

The study team will monitor adherence by reviewing each participant's dietary log, CGM data, and insulin pump data. The team will conduct a 30 to 60-minute telephone session (either via Facetime, Skype, or phone call) with the participant. The study team will review with the participants their nutritional intake and reinforce key concepts from the diet to which they are assigned (LCD or SCD). If the CGM is being worn less than 80% of the time or insulin pump is not being used to record more than 2 meals per day, the study team will troubleshoot the reason for suboptimal adherence with the participant.

Participants in groups 1 and 2 will be asked to complete nutritional tracking in the smartphone app during this time. Participants in group 3 will be asked to complete a blood sugar and exercise log.

In the event that study visit 3 occurs more than 14 weeks after study visit 2, we will conduct an additional telephone visit at week 12. We will

continue to conduct a telephone visit every 4 weeks after week 12 until the participant has completed study visit 3.

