6.1.6 Study Visit 3 (Week 12)

This visit will again correspond with the participant's routine diabetes follow up at the Eskind Diabetes Center or Vanderbilt Children's Endocrinology Franklin clinic with their primary endocrinologist.

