7.1.1 Suboptimal growth

Adherence to a low carbohydrate diet has the potential to result in a low total caloric intake and lead to suboptimal growth. One small case series describes outcomes in 6 pediatric patients who consumed between 22 – 75 grams of carbohydrates per day, including poor linear growth velocity¹³. However, both diet plans will be designed to maintain weight by using the Institute of Medicine or similar formula to calculate each participant's individual estimated energy requirement and will provide a significantly larger number of grams of carbohydrates per day than the previously described case series. Anthropomorphic measures will be taken at each study visit and participants will be removed from the study if they experience weight loss more than 10% from baseline.

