9.0 Study Withdrawal/Discontinuation

Subjects will be free to withdraw from the study at any time, which will be made clear at enrollment. Subjects will be withdrawn from the study if:

Pregnancy is detected

- The PI's (or designated MD, NP, or PA KSP) medical judgement is that participation places the subject at risk for harm

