10.0 Statistical Considerations

10.1 Recruitment and Sample Size Justification

We have targeted an accrual of 40 participants in this pilot study to achieve two goals. First, we require a sufficient number of participants to estimate the effect size and variance of the LCD as a means to reduce HbA1c in T1DM in a future definitive trial. We utilized the method of Whitehead et al. to estimate our pilot study's optimum accrual, which proposes stepped increases in sample size based on the anticipated standard difference, d, between interventions 41,42 . We defined the minimum important difference (MID) in Δ HbA1c between LCD and SCD interventions as 0.3% and estimated a pooled SD of 0.8% based on our literature review9. If d=MID/SDpooled=0.3%/0.8%=0.38, a sample size of 20 participants per arm will optimize future sample size calculations for the definitive study, while allowing for up to 40% dropout. Second, this sample size allows for up to 4 degrees of freedom in multivariable linear regression analysis.

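### Participants removed for DKA, severe hypoglycemia or weight loss have no planned Visit 3, so those removed before week 12 would probably lack their only post-baseline HbA1c, LDL-P and QOL values

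*Combined protocol and SAP*

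**What the plan says.** Section 6.1.4 sets the removal rule. Participants "will be removed from the research protocol in the event of any of the following: weight loss more than 10% from baseline", and the same applies after any DKA or severe hypoglycemia. The rule covers all three groups. Section 7.1.1 repeats it for one trigger only, in firmer terms: "participants will be removed from the study if they experience weight loss more than 10% from baseline".

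The outcomes have two time points. For Aim 1, section 2.0 says "we will obtain HbA1c at baseline and at 12 weeks after the nutrition intervention". For Aim 2 the primary outcome is "change in total LDL-P from baseline to 12 weeks after the nutrition intervention". The quality-of-life surveys follow the same schedule. Of the contacts in between, at weeks 2, 4 and 8, section 6.1.5 says "The team will conduct a 30 to 60-minute telephone session".

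Section 9.0 opens its list with "Subjects will be withdrawn from the study if" and then gives pregnancy and medical judgement. It does not mention the 6.1.4 triggers. Section 10.1 sets the sample size "while allowing for up to 40% dropout".

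**The concern.** DKA and severe hypoglycemia occur after randomisation and are tied to glycemic control, which is what Aim 1 measures. If participants with these events leave before Visit 3, their change scores are missing for reasons that may be related to the outcome. The comparison in 10.2 would then rest on those who had no such event. If removals, or the outcomes of those removed, differ between arms, the estimated difference is biased.

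The pilot is meant to supply an effect size and a variance for a definitive trial, so the completeness of these values matters even without a confirmatory test. The dropout allowance in 10.1 protects the number of completers. It does not protect against loss that depends on outcome.

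The safety rule itself is not in question, and how missing data are handled in general is a separate matter.

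**Working it through.** **Can a removed participant still have an outcome value?**

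- Visit 2 (6.1.3.2, 6.1.3.5): HbA1c, NMR lipoprofile and surveys. This is the baseline.
- Weeks 2, 4 and 8 (6.1.5): telephone contacts with no blood draw and no surveys.
- Visit 3 (6.1.6.2, 6.1.6.5): HbA1c, NMR lipoprofile and surveys. This is the only post-baseline collection.
- Section 8.5: follow-up or documentation until an SAE resolves, not trial outcomes.
- Section 9.0: no early-termination visit and no outcome collection after withdrawal.
- Section 10.2: t-tests and regressions on change from baseline, with no analysis population that would retain removed participants.

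**By trigger**

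- *Weight loss.* Leaving the study is explicit (7.1.1). However, the study measures weight at its visits, and the only in-person visit after baseline is Visit 3, where blood and surveys are taken the same day. Data are lost only if the participant reports the loss between visits.
- *DKA and severe hypoglycemia.* These can happen at any time, and participants are told to contact the team. Leaving the study is the natural reading of 6.1.4, but what follows removal is not stated. These two triggers are the main route to missing values.

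**Size, for HbA1c**

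Inputs from the plan:

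- Minimum important difference 0.3 and SD 0.8 (10.1). The plan's own ratio reproduces: 0.3/0.8 = 0.375, stated as 0.38.
- Arm size n = 15 (2.0, 6.1.1.6) or n = 20 (10.1). Both are shown.

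Assumption, not in the documents: the removed participant's change would have differed from the mean of the others in the arm by D = 0.8 to 1.6 points, that is 1 to 2 SD, in either direction.

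If the other n − 1 participants have mean m, the full-arm mean is [(n − 1)m + (m + D)]/n = m + D/n. Losing that participant therefore shifts the arm mean, and the between-arm difference, by D/n in size.

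| | n = 15 | n = 20 |
|---|---|---|
| Shift at D = 0.8 | 0.8/15 = 0.053 | 0.8/20 = 0.040 |
| Shift at D = 1.6 | 1.6/15 = 0.107 | 1.6/20 = 0.080 |
| SE of difference, 0.8 × √(2/n) | 0.292 | 0.253 |
| Shift as a share of SE | 0.18 to 0.37 | 0.16 to 0.32 |
| 95% CI half-width, t(0.975, 2n − 2) × SE | 0.598 | 0.512 |
| Gap D needed for a shift of 0.3 (0.3 × n) | 4.5 points | 6.0 points |

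The last row equals 4.5/0.8 = 5.6 SD and 6.0/0.8 = 7.5 SD, which is implausible for one participant. The sign of the shift reverses if D is negative. Equal removals with equal gaps in both arms cancel to zero.

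The documents give no SD or important difference for LDL-P or QOL, so no size is offered for those two.

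**The case against.** The strongest case against is that this is a gap in wording with little numerical effect. The plan says only that participants leave the research protocol after DKA or severe hypoglycemia, which could mean stopping the intervention. The one trigger with explicit study exit is the one least likely to cost a Visit 3 value. The protocol expects no extra hypoglycemia from the low-carbohydrate diet (7.1.2) and usual DKA rates (7.1.3), and with similar arms the bias is about zero. Of Visit 3, section 6.1.6 says "This visit will again correspond with the participant's routine diabetes follow up", so a clinic HbA1c may exist anyway.

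Most of this stands, and it sets the severity. It does not remove the point. Nothing plans to use a clinic HbA1c for a removed participant, and LDL-P and QOL depend on study procedures. Staff who follow 6.1.4 as written have no instruction to collect outcomes after removal.

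A reader might infer that the protocol orders study exit for all three triggers, so that the data will certainly be missing. The text does not go that far: exit is explicit for weight loss only. A reader might also apply the event rates from the very-low-carbohydrate survey cited in 7.1.2 and 7.1.3 to predict how many will be removed. That is not supported either: the survey's time frame is not given, and the protocol expects considerably lower hypoglycemia rates and DKA rates no higher than usual. No expected count is claimed here.

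**Conclusion.** The point holds, at minor severity. No section plans outcome collection after removal under 6.1.4, and a participant removed before week 12, mainly for DKA or severe hypoglycemia, would probably lack all three post-baseline values.

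Under the assumed gap, one removal in one arm moves the HbA1c difference by about 0.04 to 0.11 points, well inside a confidence interval half-width of about 0.5 to 0.6. The result rests on the natural reading of 6.1.4, on the assumed gap, and on removals being unequal between arms.

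A reader might infer that the rule favours one diet. The documents do not support a direction: a participant with DKA may have had a worse HbA1c and one with severe hypoglycemia a lower one, and no arm is expected to have more of either event.

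**What to change.** - **6.1.4 and 7.1.1:** replace removal with stopping the study intervention for safety. In groups 1 and 2 this means the assigned diet with its telephone coaching and text messages. In group 3, which has no assigned diet, it means the education sessions and texts. Keep the participant in follow-up through Visit 3 (HbA1c, NMR lipids, surveys) unless consent is withdrawn.
- **9.0:** cross-refer to these triggers as discontinuation of the intervention, not withdrawal from the study.
- **10.2:** analyse all available week-12 values by randomised group regardless of discontinuation, and report the triggering events by arm.

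The cost is an amendment and a change of consent wording. Added burden is small because Visit 3 falls on a routine clinic visit. The estimate would include participants who stopped the intervention, so it would be slightly diluted as a measure of the diet's effect when followed.

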6.1.4.1 Adherence monitoring

The study team will monitor adherence by reviewing each participant's dietary log, CGM data, and insulin pump data in an ongoing fashion. Should the research team detect suboptimal adherence a member of the team will contact the participant to help troubleshoot the reason for the suboptimal adherence.

6.1.4.2 Text Messaging

Participants will receive text messages 2 to 4 times per week³⁶ that will provide reminders regarding key components of the dietary intervention, encouragement regarding diabetes management, and general positive quotes. The study team will create a bank of 50 text messages for each dietary intervention (LCD and SCD), and participants will receive 2 to 4 of these text messages per week. Examples of message content include: "Try a breakfast high in protein! An omelet with a side of bacon would be a great choice" and "The only way of finding limits of the possible is by going beyond them and into the impossible – Arthur C. Clarke." The text message will be sent using the text messaging feature in RedCap with the Twilio messaging service and will contain no protected health information. Text messaging will continue until participants have completed study visit 3.

6.1.5 Telephone Visits (Weeks 2, 4, and 8)

The study team will monitor adherence by reviewing each participant's dietary log, CGM data, and insulin pump data. The team will conduct a 30 to 60-minute telephone session (either via Facetime, Skype, or phone call) with the participant. The study team will review with the participants their nutritional intake and reinforce key concepts from the diet to which they are assigned (LCD or SCD). If the CGM is being worn less than 80% of the time or insulin pump is not being used to record more than 2 meals per day, the study team will troubleshoot the reason for suboptimal adherence with the participant.

Participants in groups 1 and 2 will be asked to complete nutritional tracking in the smartphone app during this time. Participants in group 3 will be asked to complete a blood sugar and exercise log.

In the event that study visit 3 occurs more than 14 weeks after study visit 2, we will conduct an additional telephone visit at week 12. We will

continue to conduct a telephone visit every 4 weeks after week 12 until the participant has completed study visit 3.

6.1.6 Study Visit 3 (Week 12)

This visit will again correspond with the participant's routine diabetes follow up at the Eskind Diabetes Center or Vanderbilt Children's Endocrinology Franklin clinic with their primary endocrinologist.

6.1.6.1 History and Physical Exam

The PI or designee will review each subject's clinical history, perform a physical exam, and take anthropometric measurements.

6.1.6.2 Blood draw

Blood will be drawn from each participant and the following labs obtained:

- HbA1c
- Beta hydroxybutyrate
- NMR spectroscopy lipoprofile.

6.1.6.3 Continuous glucose monitor and insulin pump data collection

Continuous glucose monitor and insulin pump will be downloaded into a HIPAA and FDA-compliant cloud-based, data-integration platform such as Dexcom Clarity, Medtronic Carelink, or Tidepool.

Information that will be collected from the continuous glucose monitor download will include (but not be limited to):

- Percent of time spent above the glycemic target of 140 mg/dL
- Percent of time spent in the glycemic target of 70 140 mg/dL
- Percent of time spent below the glycemic target of 70 mg/dL
- Percent of time spent in hypoglycemia below 50 mg/dL
- Average blood glucose
- Blood glucose standard variation

Information that will be collected from the insulin pump download will include (but not be limited to):

- Average total daily dose of insulin
- Average bolus amount of insulin per day
- Average basal amount of insulin per day

6.1.6.4 Nutritional tracking smartphone application data collection

Participants in groups 1 and 2 will be asked to complete nutritional tracking in the smartphone app during this time.

Participants in group 3 will be asked to complete a blood sugar and exercise log.

Information that will be collected from the smartphone app will include (but not be limited to):

- Total number of calories consumed
- Average grams of carbohydrates consumed per day
- Average grams of fat consumed per day
- Average grams of protein consumed per day
- Additional macronutrient data

Participants will also be asked to photograph all food consumed in the 24 hours prior to the study visit. At the study visit, they will complete a 24 hour dietary recall.

6.1.6.5 Quality of life survey

Participants will complete the PedsQL, a validated QOL measure in T1DM patients and Problem Areas in Diabetes-Teen (PAID-T), a validated measure of diabetes-specific distress^{31,32}. PedsQL will be scored by a member of the research team.

Additionally, parents of participants will complete the WHO-5 Well-Being Index, a questionnaire for assessing subjective psychological well-being³⁴, and Problem Areas in Diabetes-Parent Revised version (PAID-PR), a validated measure of perceived parental burden associated with caring for a child with diabetes³³. All surveys will be scored by a member of the research team.

7.0 Risks

7.1 The following risks associated with participation are considered:

7.1.1 Suboptimal growth

Adherence to a low carbohydrate diet has the potential to result in a low total caloric intake and lead to suboptimal growth. One small case series describes outcomes in 6 pediatric patients who consumed between 22 – 75 grams of carbohydrates per day, including poor linear growth velocity¹³. However, both diet plans will be designed to maintain weight by using the Institute of Medicine or similar formula to calculate each participant's individual estimated energy requirement and will provide a significantly larger number of grams of carbohydrates per day than the previously described case series. Anthropomorphic measures will be taken at each study visit and participants will be removed from the study if they experience weight loss more than 10% from baseline.

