6.1.3.6 Diet Instructions

From weeks 0 to 12, research participants in groups 1 and 2 will consume a weight-maintaining diet designed by the Vanderbilt Diet, Body Composition, and Human Metabolism Core and the research team.

The research team will discuss food preferences with each participant to design diet plan with standard macronutrient contents. The Institute of Medicine formula⁷ or similar formula will be used to calculate the estimated energy requirement (EER).

EER for males (kcal/day) = $662 - (9.53 \times \text{age [y]}) + \text{PA} \times (15.91 \times \text{weight [kg]} + 539.6 \times \text{height [m]}).$

Where PA is the physical activity coefficient:

PA = 1.00 if PAL is estimated to be \geq 1.0 < 1.4 (sedentary)

PA = 1.11 if PAL is estimated to be \geq 1.4 < 1.6 (low active)

PA = 1.25 if PAL is estimated to be \geq 1.6 < 1.9 (active)

PA = 1.48 if PAL is estimated to be \geq 1.9 < 2.5 (very active)

[figure not shown]
EER for females (kcal/day) = $354 - (6.91 \times age [y]) + PA \times (9.36 \times weight [kg] + 726 \times height [m])$

Where PA is the physical activity coefficient:

PA = 1.00 if PAL is estimated to be \geq 1.0 < 1.4 (sedentary)

PA = 1.12 if PAL is estimated to be \geq 1.4 < 1.6 (low active)

PA = 1.27 if PAL is estimated to be \geq 1.6 < 1.9 (active)

PA = 1.45 if PAL is estimated to be \geq 1.9 < 2.5 (very active)

Figure 2: Macronutrient Content of SCD and LCD

The study team will devise two isocaloric diet plans for each participant in groups 1 and 2. One plan, the standard carbohydrate diet (SCD), will reflect the acceptable macronutrient distribution range of the Institute of Medicine's Recommendations for Nutrition: carbohydrate (45%–65% of energy), protein (10%–30% of energy), and fat (25%–35% of energy) (figure 2).⁷ The other plan, the low carbohydrate diet (LCD), will reduce the percent caloric intake from carbohydrates and replace that amount with calories from dietary fat. Thus with the LCD, 45%–65% of energy will come from fat, 10-30% of energy will come from protein, and 25%–35% of energy will come from carbohydrates (figure 2).

Group 3 will serve as a control that receives the same number of education sessions as groups 1 and 2 to teach general diabetes management but without specific dietary recommendations. This study design will allow for discrimination of the effect of the composition of the diet versus the effect of receiving any nutritional prescription.

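### The removal rule for weight loss above 10% has no scheduled weight behind it between visit 2 and visit 3, so during the diet it rests on self-report that the protocol text does not support

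*Combined protocol and SAP*

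**What the plan says.** **The rule.** Section 7.1.1 recognises that a low carbohydrate diet may lead to low caloric intake and poor growth. It answers that the diets are designed to maintain weight, and that anthropometric "measures will be taken at each study visit and participants will be removed from the study if they experience weight loss more than 10" per cent from baseline.

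Section 6.1.4, which governs the period between visits 2 and 3, gives a second route: "Participants will be instructed to contact the research team and will be removed from the research protocol" in the event of "weight loss more than 10% from baseline or any episode of DKA or severe hypoglycemia".

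**The exposure.** Section 6.1.3.6: "From weeks 0 to 12, research participants in groups 1 and 2 will consume a weight-maintaining diet". Section 6.1.4.2 adds: "Text messaging will continue until participants have completed study visit 3".

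**The measurements.** Anthropometrics are listed in sections 6.1.1.2 (visit 1), 6.1.3.1 (visit 2) and 6.1.6.1 (visit 3). Between visits 2 and 3, section 6.1.4.1 has staff review each participant's "dietary log, CGM data, and insulin pump data in an ongoing fashion". Section 6.1.5 describes the contacts at weeks 2, 4 and 8 as remote: "The team will conduct a 30 to 60-minute telephone session (either via Facetime, Skype, or phone call"). They review the same three data sources.

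**A late final visit.** Section 6.1.5 foresees this ("In the event that study visit 3 occurs more than 14 weeks after study visit 2") and adds telephone visits at week 12 and every four weeks after that. It adds no clinic visit and states no upper limit.

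**The concern.** A stopping rule protects a participant only if someone can see the threshold being crossed while the exposure can still be stopped. Here the first scheduled weight after the diet starts is taken at the visit that ends it. Until then, the rule works only if a participant notices and reports a percentage weight loss.

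The neighbouring risks are handled differently. For hypoglycemia, section 7.1.2 provides continuous CGM, a glucose level below 70 as the trigger to contact the team, and a glucagon kit. For ketoacidosis, section 7.1.3 lists symptoms and home urine ketones. Both can be recognised between visits with the means given. A 10% weight loss cannot be known without a scale, and the text provides none.

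At stake is a safeguard for adolescents, in a study whose own risk section names low intake and growth as a hazard.

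**Working it through.** The plan gives no figure to reproduce. The check is a count of scheduled weights, then the length of the gaps.

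**Step 1. Every scheduled contact.**

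| Contact | Section | Time | Mode | Anthropometrics listed |
|---|---|---|---|---|
| Visit 1 | 6.1.1.2 | week -2 | clinic | yes |
| Visit 2 | 6.1.3.1 | week 0 | clinic | yes |
| Telephone visits | 6.1.5 | weeks 2, 4, 8 | remote | no |
| Added telephone visits | 6.1.5 | week 12, then every 4 weeks, if visit 3 is beyond week 14 | remote | no |
| Visit 3 | 6.1.6.1 | week 12 | clinic | yes |

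Scheduled weights after visit 2 and before visit 3: 0. Routine care adds none, because visits 2 and 3 are themselves the routine diabetes follow-ups (6.1.3, 6.1.6). The words about measuring at each study visit cannot sensibly cover the telephone visits, which are named separately and are remote.

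**Step 2. Gaps as written.**
- Visit 3 on time: 12 × 7 = 84 days.
- Visit 3 beyond week 14: more than 14 × 7 = 98 days, with no stated maximum.

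**Step 3. Gaps with a weight at each existing call.**
- Weeks 0-2 and 2-4: 14 days each.
- Weeks 4-8 and 8-12: 28 days each, so the longest gap is 28 days with visit 3 on time.
- Visit 3 beyond week 14: the added calls keep the four-week spacing, again 28 days.
- Visit 3 between weeks 12 and 14: no week 12 call is triggered, so the last gap can reach (14 - 8) × 7 = 42 days.

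**Step 4. Could the threshold be crossed inside 84 days? (Illustration only.)** The documents supply the EER formulas and activity coefficients (6.1.3.6). Body sizes and an energy value of k = 6,000 to 7,700 kcal per kg lost are assumptions. The sustained shortfall needed to lose 10% by day 84, as a share of EER, is

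shortfall = 0.10 × weight × k / (84 × EER).

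- Lowest of four assumed bodies of 48-60 kg: boy, 13 years, 50 kg, 1.60 m, very active, k = 6,000. EER = 662 - 9.53 × 13 + 1.48 × (15.91 × 50 + 539.6 × 1.60) = 2,993 kcal. Shortfall = 30,000 / (84 × 2,993) = 11.9%.
- Highest of the four: girl, 15 years, 55 kg, 1.62 m, sedentary, k = 7,700. EER = 354 - 6.91 × 15 + 1.00 × (9.36 × 55 + 726 × 1.62) = 1,941 kcal. Shortfall = 42,350 / (84 × 1,941) = 26.0%.
- Two heavier assumed bodies (85 and 90 kg): 15.9-34.9%.

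Days to a 10% loss. Each range covers EER held fixed and EER falling as weight falls.

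| Sustained shortfall | Four bodies of 48-60 kg | Two heavier bodies |
|---|---|---|
| 10% | 100-254 | beyond day 84 |
| 20% | 50-117 | 67-162 |
| 30% | 33-76 | 45-104 |

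A 10% shortfall does not reach the rule by day 84. A 20% shortfall straddles day 84. At 30% the four lighter bodies cross before visit 3, and the heavier ones may or may not. The threshold can therefore be crossed during the diet under a large sustained deficit, but these figures say nothing about how likely that is.

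**The case against.** **The rule is not inoperative.** A reader might infer that, because staff first weigh participants when the diet is over, the rule spares nobody any exposure. The documents do not support that. Section 6.1.4 is a between-visit rule under which a participant who reports a loss is removed then. What stands is that this route has no weighing behind it in the text.

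**Silence is limited evidence.** Section 5.4 refers to pre-visit tasks set out in the consent documentation and in written instructions to participants. The consent pages and the timeline figure are not available here, and a home-weighing instruction could sit there. The point is therefore confined to the protocol text, where the monitoring tasks in 6.1.4.1 and 6.1.5 are described without weight.

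**Other safeguards address the cause.** The diets are set to the estimated energy requirement, the app records total calories, intake is discussed at each call, and section 9.0 allows withdrawal on medical judgement. These are real but partial. App tracking is described as intermittent (6.1.1.3), group 3 is asked for a blood sugar and exercise log instead (6.1.5), and a log estimates intake while the rule needs weight.

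**Two further inferences fail.** A reader might call the baseline ambiguous between visits 1 and 2, but the Aim 3 text in section 2.0 places baseline at week 0. A reader might also infer that removal at visit 3 would distort the HbA1c comparison. Nothing says that such a participant's data are discarded. HbA1c is drawn at that same visit, and the order in which the exam and blood draw are listed proves nothing. Any figure for the shift would also need an assumed displacement of that participant's HbA1c change.

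**Conclusion.** The point holds as a modest operational gap in a safety rule. Between visit 2 and visit 3 no weight is scheduled, for 84 days or for more than 98 if visit 3 is late. The only numeric safeguard for low intake and suboptimal growth relies throughout that time on self-report, without an instruction to weigh or a question that would elicit a weight.

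This rests on two readings: that the anthropometric measurements include weight, and that the participant materials not seen here add no home weighing. It does not rest on the energy-deficit figures, which depend on assumed bodies and give no likelihood of a 10% loss. Since both diets are meant to maintain weight, such a loss may well be uncommon. The case for acting is that the remedy is cheap, not that harm is expected.

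**What to change.** **Change to 6.1.5, with a cross-reference in 6.1.4 and 7.1.1.** At each telephone visit (weeks 2, 4, 8 and any added later), in all three groups, record a home weight reported by the participant or a parent, with refusal allowed. Compare it with the visit 2 weight. Confirm any apparent loss above 10% with a clinic weight before removal.

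**Gain.** The longest interval without a weight falls from 84 or more days to about 28 (up to 42 if visit 3 falls between weeks 12 and 14). A loss that passes 10% only after the week 8 call would still first be seen at visit 3 when that visit is on time.

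**Cost.** One question per existing call, one REDCap field and an occasional confirmatory clinic weight. No new visit is scheduled. Home scales are noisy and may differ from the clinic scale, which is why clinic confirmation comes before removal. Weighing may be unwelcome for some adolescents, hence parent reporting and the right to refuse. Asking all three groups keeps contact equal.

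**Optional.** The sponsor may add a clinician review at a 5% fall, fixed before enrolment. The 5% level is a judgement, not derived from the documents. If home-to-home change has an SD of 1.5-2.5% of body weight (assumed), a weight-stable participant triggers it with probability Φ(-5/SD), which is 0.04-2.3% per call. Over three independent calls that is 1 - (1 - p)³, or 0.1-6.7%.
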